4.1 Background and Rationale

4.1.1 Background

Achromatopsia is a recessively inherited condition characterised by a lack of cone photoreceptor function resulting in impairment of colour vision and visual acuity, central scotoma often with eccentric fixation, disabling hypersensitivity to light (photophobia) and involuntary eye movements (nystagmus), (Kohl *et al.*, 2013; Aboshiha *et al.*, 2015; Michaelides *et al.*, 2004). In the United States, Achromatopsia is estimated to affect 9,566 individuals (Judd, 1943; Sharpe *et al.*, 1990; Sharpe *et al.*, 1999), in 50% of whom (4,783) the condition results from mutations in the *CNGB3* gene (Kohl *et al.*, 2005).

Achromatopsia resulting from mutations in *CNGB3* has several characteristics that make it a good candidate disease to demonstrate proof-of-principle in a first-in-man trial of gene therapy for photoreceptor disease. Effective improvement in cone photoreceptor function, which is otherwise absent (or markedly reduced) in this condition, would provide a clear, rapid and reliable measure of outcome. In addition, achromatopsia is largely non-progressive and the extended survival of cones, despite their profound lack of function, presents a wide window of opportunity during which gene supplementation could lead to significant benefit in cone-mediated vision. Although younger individuals may benefit most from gene supplementation therapy by virtue of their greater visual plasticity, we anticipate that the intervention may offer benefit across a range of ages and we aim to define this range. For this reason, participants of various ages will be included; children (as defined by age in section 4.3) will be included once an acceptable safety profile has been established in adults.

4.1.2 Pre-clinical data

In preclinical studies using a murine model of *CNGB3*-deficiency, we have demonstrated that delivery of a functional copy of the h*CNGB3* cDNA sequence to cone photoreceptors is associated with substantial improvements in cone function and morphology (Carvalho, *et al* 2011). Subretinal injection of AAV2/8-hCARp.h*CNGB3* of (2.0×10^{12} vg/mL) restores *CNGB3* protein in cone outer segments, prolongs cone survival, and substantially improves photopic ERG amplitudes (cone-mediated responses on electroretinography) in mice ranging in age from 15 days to 6 months. In younger animals improved cone function results in a complete recovery of cone-mediated vision as assessed by optomotor responses. These findings in mice demonstrate one of the most effective rescues of an animal model of a photoreceptor defect reported to date, suggesting that achromatopsia in humans may also benefit from gene supplementation therapy. These results are supported by a study by Komaromy and coworkers, demonstrating successful gene supplementation therapy in a dog model of the same condition (Komaromy, *et al* 2010).

4.1.3 Clinical data

This protocol describes our group's 3rd clinical trial of a gene supplementation therapy for inherited retinal disease using a recombinant AAV (rAAV) vector. In the first gene therapy trial (Bainbridge, *et al* 2008) 12 participants with severe early onset retinal dystrophy caused by mutations in the gene encoding RPE65 were administered rAAV vector subretinally. Vector administration was generally well tolerated and 6 of the 12 participants benefitted with improved visual function to varying

Gene Therapy for Achromatopsia (*CNGB3*)

extents during the first year. However, longer-term follow-up demonstrated that progressive degeneration continued and maximal improvements in retinal sensitivity were not maintained (Bainbridge, *et al* 2015). Similar observations have been described in other independent trials where rAAV2/2 vectors were administered for the same condition by sub retinal administration (Maguire, *et al* 2008; Cideciyan, *et al* 2008; Cideciyan, *et al* 2013). In these studies, subretinal administration of rAAV vectors resulted in visual improvement without significant safety concerns. We are currently investigating the safety and potential efficacy of a new optimized rAAV2/5 vector for delivery of *RPE65* in a trial with a similar design and protocol to this proposed trial [REDACTED] in up to 27 adults and children with retinal dystrophy caused by mutations in *RPE65*.

4.1.4 Rationale

We predict that in *CNGB3*-related Achromatopsia, delivery of a cDNA sequence encoding a functional *CNGB3* protein using gene supplementation will lead to measurable improvements in visual function within 6 months.

There is currently no effective treatment available for most hereditary retinal disorders including achromatopsia. This condition is characterised by absent (or markedly reduced) cone function resulting in profound reduction in visual acuity, complete lack of (or markedly reduced) colour vision, marked photophobia and nystagmus. The *CNGB3* gene encodes the beta subunit of the cone photoreceptor-specific cGMP-gated cation channel, which is critical for cellular responses to light. Absence of this beta subunit results in absent/extremely poor cone function and hence very poor daylight vision. Although loss of cone photoreceptor cells may occur in a limited number of patients, the rate of cell death is very slow, resulting in retinas containing surviving but non-functioning cones. Improvement of cone function by provision of *CNGB3* could provide a clear, rapid and reliable measure of outcome. Furthermore, the relatively non-progressive nature of Achromatopsia, with extended survival of cone photoreceptors, means that the window of opportunity for effective intervention by gene supplementation may extend into adulthood.

However, since achromatopsia results in marked visual impairment from birth, associated abnormal development of physiological cone-dependent neuronal circuits, including that of the visual cortex, may limit the potential for older individuals to benefit from therapeutic restoration of retinal function. Since visual cortical plasticity is known to be greater in younger children, we will recruit children once an acceptable safety profile has been defined in adults. Older participants might benefit with relief from photophobia even if limited cortical plasticity affects the potential for improved acuity or colour vision.

4.1.5 Assessment and management of risk

A gene therapy trial in human volunteers should not put the participants at disproportionate risk and for this reason should be restricted to individuals with serious disorders where effective treatments are not available. *CNGB3*-related Achromatopsia results in profound sight impairment from birth or early infancy. The condition is currently untreatable, but there is a real possibility that gene therapy could offer a significant benefit in terms of improved sight and quality of life (QOL), based on our own experience from the first clinical trial for ocular gene therapy, subsequent ocular gene therapy trials elsewhere (Maguire, *et al* 2008; Cideciyan, *et al* 2008 and 2013), and pre-clinical data demonstrating improved outcome in *CNGB3*-related achromatopsia. Possible benefits of improved

Gene Therapy for Achromatopsia (CNGB3)

cone-photoreceptor function include, improved visual acuity, improved colour perception, and relief from disabling photophobia.

The safety of the proposed approach will be enhanced by restricting transgene expression to the target tissue by virtue of rAAV vector tropism and the cone-specific promoter sequence used, and by restricting the intervention to one eye only in each participant. The risk of adverse effects will be further minimised by minimising the volume of vector suspension administered and by targeting it surgically to the cone rich region of the central retina.

Risks to participant safety in relation to the ATIMP is classified using the MHRA definition as Type C (Markedly higher than the risk of standard medical care). General risk management includes the detailed review of all participants, appropriate intervals between ATIMP administration to successive participants, the dose escalation plan, and limiting the risks to children by initially demonstrating an acceptable safety profile in adults. In addition, the schedule of participants' assessments has been designed to identify the short term and the longer-term risks. Details of specific risks and their management strategies are outlined below.

4.1.5.1 Risk of immune responses to AAV2/8-hCAR.hCNGB3

The main risk of inflammation will be during the early postoperative period after ATIMP administration, before vector capsids are degraded. The risk of inflammation during this period will be minimised by pre- and post-operative prophylactic treatment using topical and systemic corticosteroids. Persistent intraocular inflammation will be managed by topical corticosteroid therapy, with systemic corticosteroids where indicated.

The risk of inflammation is likely to be highest during the early postoperative period after ATIMP administration, before vector capsids are degraded. The risk of inflammation during this period will be minimised by pre- and post-operative prophylactic administration of topical and systemic corticosteroids. In our first clinical trial of gene therapy, intra-ocular delivery of an AAV2/2 vector was followed by transient intraocular inflammation in 3 of 12 participants. In our subsequent trial of gene therapy, intraocular administration of an AAV2/5 has been well tolerated in majority of participants to date. A minority of participants developed an episode of intraocular inflammation involving the posterior segment, which responded to further administration of systemic corticosteroids.

4.1.5.2 Risk of vector transmission to other organs

Biodistribution studies suggest that following subretinal injection of AAV, anterograde and trans-synaptic transport of small amounts of vector genome from the retina to central visual structures may occur (Stieger, *et al* 2008). This is considered most likely to result from off target transduction of retinal ganglion cells following reflux of vector suspension into the vitreous. Since only tiny amounts of vector are likely to reach the brain and a cone photoreceptor-specific promoter will be used, the possibility of transgene expression causing toxicity in the brain is considered to be highly unlikely. Minimal vector amounts (i.e. a few hundred vector genome copies) might be traced in other organs like lymph nodes, spleen and liver but similarly to the brain; transgene expression causing toxicity is highly unlikely due to the cone photoreceptor-specific promoter.

4.1.5.3 Risks of insertional mutagenesis and oncogenesis

The possibility of oncogenic events due to vector-mediated insertional mutagenesis cannot be excluded with certainty, but available evidence suggests it to be unlikely given that (i) AAV vector genomes integrate into host chromosomes at a very low frequency (Nowrouzi, *et al* 2012), (ii) a limited number of AAV particles will be administered, and (iii) the eye predominantly contains non-dividing cells and consequently ocular tumours are very rare. Furthermore, oncogenesis has not been reported following injection of AAV into thousands of rodent eyes. Even when we injected AAV vectors intraocularly in a large number of tumour-prone *p53*^{-/-} mice, we found no evidence of malignant transformation of retinal cells (Balaggan, *et al* 2012). In the highly unlikely event that an intraocular tumour does arise, the comprehensive monitoring procedures described in Section 5.4.2.3 of the protocol will enable early detection and thus prompt appropriate management.

4.1.5.4 Risk of germline transmission

The risk of inadvertent germline transmission is very small. In a number of studies using a variety of animal models involving various routes of administration, including intraocular injection, inadvertent germline transmission by AAV vectors has not been detected. Similarly, we detected no vector genomes in semen in our previous retinal gene therapy clinical trial (Bainbridge, *et al* 2008). Systemic intravascular administration of rAAV2 to deliver factor IX in haemophilia B, can lead to vector sequences detectable in semen, though not sperm for a short period (Manno *et al* 2006). However, in this instance doses ranging from 8×10^{10} to 2×10^{12} vg/kg were administered, considerably higher than the doses proposed for subretinal injection in this study. Whilst this indicates there may be some potential for inadvertent germline transmission following the systemic delivery of high doses of vector, the possibility of such an event following the microsurgical delivery of tiny amounts of vector to intraocular compartments is considered to be remote. Participants who are fertile and sexually active will be requested to use double-barrier contraception for at least 12 months following ATIMP administration.

4.1.5.5 Risk of surgical adverse effects

The risk of significant surgical adverse effects is similar to the standard surgical care for other common forms of vitreo-retinal disorders. To manage the risk of surgical adverse events, only highly experienced surgeons will perform the procedure. Complications of surgery are typically managed effectively by medication or further surgical intervention but can rarely result in lasting harm to sight. The risk of lasting severe impairment of sight from vitrectomy surgery is approximately 1 in 1000. We have identified some reduction in outer retinal thickness and deterioration in acuity in 2 of the 12 participants in our previous clinical trial, believed to result from temporary retinal detachment which is a deliberate consequence of targeted administration of the vector suspension, but no other significant surgical adverse effects.

Delivery of ATIMP to the subretinal space will be performed by standard surgical vitrectomy. This will involve a 3-port pars plana vitrectomy followed by injection of ATIMP using a fine cannula through small retinotomies, resulting in a temporary retinal detachment. Previous gene therapy clinical trials have shown that the bleb of subretinal ATIMP suspension can be expected to resolve spontaneously over the course of the first 24 to 48 hours postoperatively as the fluid is absorbed by the underlying retinal pigment epithelium.

Gene Therapy for Achromatopsia (*CNGB3*)

Potential complications of surgery specifically include persistence of the subretinal vector bleb, the development of retinal tears, and persistent postoperative intraocular inflammation. We will minimise any risk to visual function by limiting ATIMP delivery to the area of retina most likely to benefit, and by leaving the contralateral eye untreated. Retinal detachment caused by persistent vector bleb or intraoperative retinal tear is expected to occur in fewer than 1 in 100 procedures and can be effectively managed in the majority by retinopexy, with or without intraocular tamponade. Vitrectomy surgery is a standard technique, commonly performed for a wide range of indications. Injection of fluids under the retina is less commonly performed but is a standard step in surgery for subretinal haemorrhage, and an adjunctive technique in the management of retinal detachment.

4.1.5.6 Risk of adverse effects of short-term corticosteroids

Candidates will be screened for contra-indications to transient immune suppression by corticosteroids; in particular, a history of uncontrolled hypertension, diabetes mellitus, tuberculosis, renal impairment, osteoporosis, gastric ulceration, severe affective disorder and immunocompromised status. The possibility of steroid-induced adverse effects will be monitored regularly. In particular, blood pressure and blood glucose will be measured, as will renal function and liver function (at baseline, 1 day, 7 days, 2 weeks and 4 weeks after surgery).

4.1.5.7 Risks of investigations performed during assessment and follow up

The majority of investigations are non-invasive routine clinical tests and present no significant risk. Venepuncture causes temporary discomfort, occasionally bruising/swelling and rarely infection at the site of puncture.

4.1.5.8 Risk of rod photoreceptor dysfunction

The aim of the intervention is to improve the function of cone photoreceptor cells. Rod photoreceptors exposed to the ATIMP are not expected to benefit but may be subject to adverse effects of the surgical intervention or ATIMP. We plan to minimize any adverse effect by targeting the ATIMP to the central retina where the cone photoreceptors predominate. In addition, the use of a cone specific promoter to drive *CNGB3* expression specifically in cones, will minimise inappropriate ectopic expression in rod photoreceptors. Moreover, should cone photoreceptor-mediated vision be improved by the gene therapy, any dysfunction of rod photoreceptor cells is expected to be evident only in a dimly illuminated environment.

No rod dysfunction has been described to date in the animal models (mouse and dog) used to demonstrate the potential of gene supplementation therapy in *CNGB3*-associated achromatopsia.

4.1.5.9 Risk of thinning of the fovea

Thinning of the retina in the macula (macular thinning) has been detected in 6/10 participants after subfoveal delivery of AAV vector in our previous clinical trial. Macular thinning was typically apparent within 3 months and subsequently non-progressive. Associated thinning of the photoreceptor cell (outer nuclear) layer was evident, with variable disruption of the photoreceptor ellipsoid (inner segment) zone. Participants in the proposed trial may develop macular thinning but since the central macula comprises predominantly cone photoreceptor cells that have no function in achromatopsia, we do not expect this to affect vision adversely.

Gene Therapy for Achromatopsia (*CNGB3*)

4.1.5.10 Risk of visual imbalance

Individuals affected by achromatopsia have severe sight impairment with no colour perception from birth. Improvement of retinal function by intervention later in development is expected to lead to new visual experiences. While these are expected to be positive, unpleasant visual sensations might also be experienced.

4.1.5.11 Conclusion on the risk-benefit ratio

In summary, the risks associated with the intervention are justified by the potential for individual participants to benefit, and by the scientific value of the trial to the development of treatments for other individuals similarly affected.

4.1.6 Explanation for Choice of Comparators

There is no currently approved treatment for achromatopsia caused by mutations in *CNGB3*. The comparator will be the contralateral eye.

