5.4.2 Protocol defined clinical schedule

5.4.2.1 Baseline Assessments

A detailed assessment of visual function and retinal imaging of both eyes will be performed preoperatively as outlined in Section 5.6 (Table 2: Trial Assessments). For assessments requiring multiple baselines, testing is preferred on separate days within a maximum 6-month period to allow for day-to-day variation and test-retest variability for individual participants. However, it is acknowledged that a balance will be achieved between what is pragmatic and appropriate for the different tests on an individual basis. Each set of baseline measurements may take up to 3 days to perform in total. In some instances, results for protocol specified baseline tests may be available as a part of routine clinical examination within 6 months. As such, if the subject provides informed consent to use the results from the previously conducted tests, then these assessments will not need to be repeated at baseline.

Visual assessment results will be sent for reading and analysis to independent reading centres within the UK and US. For both sites imaging with OCT, fundus autofluorescence and fundus photography will be reviewed by the site teams but also sent for independent analysis by the [REDACTED], during the course of the trial. Adaptive optics images will be sent to the [REDACTED] for reading and Octopus perimetry and Microperimetry will be sent to the [REDACTED] reading centre. All images will be saved under pseudo anonymised patient identifiers and images will only be taken of the patient's eye to ensure that patients remain unidentified.

Gene Therapy for Achromatopsia (*CNGB3*)

Up to 10 mL of blood will be sampled in order to assess baseline levels of circulating antibodies against, AAV8 and of circulating antibodies against rAAV serotype 8 so that immunological responses to vector capsids can be determined following ATIMP administration (collectively described as serology in Table 2: Trial Assessments). We anticipate that that majority of participants will have no detectable pre-existing circulating antibodies against AAV8. The presence or absence of circulating antibodies will not affect recruitment of the participant. All serology tests will be performed at the Institutional Laboratory in the UK.

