5.4.2.2.2 Technique for intraocular administration of ATIMP

The choice of eye for ATIMP administration will be the poorer-seeing eye as identified by the participant and CI/PI taking into account ocular dominance and visual acuity.

The recombinant vector will be delivered in the form of a suspension of viral vector particles injected intraocularly (subretinally) under direct observation using an operating microscope. This procedure will include a 3-port pars plana vitrectomy followed by injection of ATIMP using a fine cannula through small retinotomies into the subretinal space.

Surgery will be performed under general anaesthesia. The eye and face will be prepared using povidone iodine solution as per routine intraocular surgery. The face and eye will be covered with an adhesive sterile plastic drape. An opening will be made at the point of the palpebral fissure and a wire speculum inserted to retract the upper and lower eyelids. The speculum and all intraocular instruments will be sterilised according to standard local operating procedures. Three pars plana sclerotomies will be sited to enable intraocular infusion, endoillumination probe and surgical instruments. The fundus will be viewed by means of a binocular indirect ophthalmoscope (BIOM) indirect viewing system or a contact lens. To minimise the possibility of unplanned retinal detachment or preretinal fibrosis, vitrectomy (aspiration of vitreous gel) will be performed using a disposable cutter.

Intraocular administration of the viral vector suspension (AAV2/8-hCARp.hCNGB3) will be performed using a subretinal cannula advanced through the retina.

Under direct visualisation, the ATIMP will be injected under the neurosensory retina, causing a localised retinal detachment with a self-sealing non-expanding retinotomy. The aim will be to target the ATIMP to the central macula. If appropriate, the bleb of ATIMP will be manipulated to the target area using a fluid-air exchange. The site and extent of the subretinal bleb of ATIMP suspension will be documented by video recording.

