5.6 Trial Assessments

Table 2: Trial assessments

	Screening	Baseline ¹			ATIMP admin	D1	D3	W1	W2	W4	W6	W12	W24
Flexibility of schedule (\pm days)		- 6 months			Day 0	\pm 0D	\pm 1D	\pm 2D	\pm 4D	\pm 7D	\pm 7D	\pm 14D	\pm 14D
Visit number	1	2	3	4	5	6	7	8	9	10	11	12	13
Informed consent	•												
Physical exam	•												
Medical history	•							•	•	•	•	•	•
Eligibility determination	•												
ATIMP administration					★								
Adverse event review		•	•	•	•	•	•	•	•	•	•	•	•
Concomitant medication review	•	•	•	•	•	•	•	•	•	•	•	•	•
Genetic screening ⁶	•												
Pregnancy test	•				•								
Vital signs ²	•	•				•		•	•	•			
Haematology		•				•		•	•	•			
Biochemistry/glucose/liver and renal function		•				•		•	•	•			
Serology		•								•		•	•
PCR						•				•			
QoL questionnaires (IVI and EQ5D-5L)		•											•
Visual acuity ³	•	•	•	•		•	•	•	•	•	•	•	•
Colour vision assessments		•	•	•								•	•
Contrast sensitivity	•	•	•	•								•	•
Reading speed		•	•	•								•	•
Static perimetry		•	•	•								•	•
Full Field Stimulus Testing		•	•	•							•	•	•
Ocular examination	•	•	•	•		•	•	•	•	•	•	•	•

CNGB3 Gene Therapy trial for Achromatopsia

	Screening	Baseline ¹			ATIMP admin	D1	D3	W1	W2	W4	W6	W12	W24
Flexibility of schedule (\pm days)		- 6 months			Day 0	\pm 0D	\pm 1D	\pm 2D	\pm 4D	\pm 7D	\pm 7D	\pm 14D	\pm 14D
Fundus photography		•				•	•	•	•	•	•	•	•
Optical coherence tomography	•	•	•	•		•	•	•	•	•	•	•	•
Adaptive optics imaging		•	•										•
Fundus autofluorescence		•	•									•	•
Pattern Electroretinography ⁴	•												•
Full field Electroretinography ⁴	•												•
Photoaversion assessments		• ⁵	• ⁵	• ⁵								•	•

¹ Baseline assessments may be performed on the same day where considered logistically and clinically appropriate

² Measurements for vital signs include: blood pressure, pulse, respiration rate, arterial oxygen saturation, temperature, height and weight

³ Visual acuity at day 1 and 3 will be assessed using the previous refraction.

⁴ ERG assessments may be performed under general anaesthesia if considered appropriate

⁵ Photoaversion Questionnaire only to be completed at one baseline visit

⁶ Not required to be repeated if previous result available from an accredited laboratory

CNGB3 Gene Therapy trial for Achromatopsia

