3.2. Baseline

In general, baseline is defined as the closest visit prior to ATIMP administration and will exclude any screening observations (unless there are no other observations prior to ATIMP administration). However, for efficacy parameters with multiple planned assessments in the baseline window, the arithmetic mean will be used as the baseline value.

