6.2. Analysis Methods

Summaries by age group, dose level and time point (and study eye when appropriate) using descriptive statistics will be provided for each outcome. Descriptive statistics such as mean, median, standard deviation, minimum, and maximum will be used to summarize continuous variables, and counts and percentages will be used to summarize categorical variables; 95% CIs may be provided for descriptive statistics. Data from each individual will also be plotted across time by age group and dose level for the treated eye compared to the untreated eye, if available. Change from baseline will be summarized, if appropriate.

Mixed linear effects models may be used to assess differences between the treated and the untreated eye with covariates including age group, dose level, time and the interaction of dose level by time. An unstructured correlation structure will be used to model within-subject correlations when possible. Possible transformations of the response (i.e., logarithm) may also be considered for some outcomes.

Sensitivity analyses with demographics such as sex and race may be explored.

Quality of life patient reported outcome measures may be used to correlate a subject's feeling about their own well-being with clinical observations. The IVI-C and IVI-A will be summarized by the 3 domains of reading and accessing information, mobility and independence, and emotional well-being. The EQ-5D-5L⁴ and EQ-5D-Y⁵ will also be summarized (see Attachment 1 for details).

For specialized ophthalmologic assessments, data may be analyzed by the expert team member(s) who are best qualified to analyze and interpret those assessments. Final data will be reported descriptively.

REFERENCES

- Goldstein JE et al. Calibrating the impact of vision impairment (IVI): creation of a sample-independent visual function measure for patient-centered outcomes research. Translational Vision Science & Technology; December 2018; Vol.7, 38
- 2. Lamoureux EL et al. The impact of vision impairment questionnaire: an evaluation of its measurement properties using Rasch analysis. Invest Ophthalmology & Vision Science; November 2006; 47(11):4732-41
- 3. Lamoureux EL et al. The impact of vision impairment questionnaire: an assessment of its domain structure using confirmatory factor analysis and Rasch analysis. Invest Ophthalmology & Vision Science. March 2007; 48(3):1001-6

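### Baseline-visit or reused clinic acuity readings that help choose the poorer-seeing eye are not kept out of the baseline, so the treated-versus-fellow change in acuity can be biased toward the vector

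*Protocol*

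**What the plan says.** Protocol 5.4.2.2.2 gives the rule for the study eye: "the poorer-seeing eye as identified by the participant and CI/PI taking into account ocular dominance and visual acuity". It names no reading, visit or date for the choice. Protocol 4.1.6 says: "The comparator will be the contralateral eye". SAP 6.1 says the efficacy objectives centre on treated versus untreated eye.

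Protocol Table 2 (5.6) has visual acuity at screening and at three baseline visits, all before dosing. On these repeats, 5.4.2.1 says "testing is preferred on separate days within a maximum 6-month period to allow for day-to-day variation and test-retest variability", while a footnote to Table 2 adds: "Baseline assessments may be performed on the same day where considered logistically and clinically appropriate". Sections 5.3.1.6 and 5.4.2.1 also let consented routine clinic results stand in for baseline tests.

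SAP 3.2 says the baseline "will exclude any screening observations (unless there are no other observations prior to ATIMP administration"), and that "for efficacy parameters with multiple planned assessments in the baseline window, the arithmetic mean will be used as the baseline value". Acuity is such a parameter. SAP 6.2 says: "Change from baseline will be summarized, if appropriate". It also allows a mixed model comparing the eyes; its listed covariates do not include the eye's baseline value.

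**The concern.** Measured acuity is true acuity plus error. When the lower-reading eye is picked for treatment, it tends to be an eye that read low by chance on those readings, and the fellow eye one that read high. If the same readings then form the baseline, the chance part is absent at the next measurement. The treated eye appears to rise and the fellow eye to fall, although nothing has happened. Subtracting baseline does not remove this; it creates it. The true pre-treatment gap between the eyes is a separate matter and does cancel in the change.

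At stake is the between-eye change in acuity, part of the contrast on which the SAP says efficacy centres. The error would favour the vector.

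**Working it through.** **Inputs from the documents.** One screening and three baseline acuity readings per eye (Protocol Table 2); baseline is the mean of the three, screening excluded (SAP 3.2); up to 36 participants, up to 18 per phase (Protocol 5.7); two-sided nominal 0.05 (SAP 6). The plan gives no SD, effect size or bias figure to reproduce.

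**Assumptions, not in the documents.** Single-reading error SD σ = 3 or 5 letters; SD of the true between-eye difference τ = 3 or 5 letters; independent errors; no systematic difference between eyes; choice on acuity alone unless stated; no vector effect.

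**Formula.** Let S be the between-eye difference used to choose the eye and e the error in the between-eye baseline difference. The expected spurious treated-minus-fellow gain is √(2/π) × Cov(e, S) / SD(S), with √(2/π) = 0.798.

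- Screening alone decides: Cov(e, S) = 0, so the gain is 0.
- Mean of three baselines decides: Cov = 2σ²/3 and Var(S) = τ² + 2σ²/3. For σ = 5, τ = 3: 16.67/√(9 + 16.67) × 0.798 = 2.62. For σ = 3, τ = 5: 6/√(25 + 6) × 0.798 = 0.86.
- All four readings decide: Cov = 2σ²/4 and Var(S) = τ² + 2σ²/4. For σ = 3, τ = 5: 4.5/√(25 + 4.5) × 0.798 = 0.66.

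Rejection rates come from 20,000 simulated trials per setting, with a paired t-test on change to one later reading, when the mean of three decides.

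| σ | τ | Gain, mean of 3 decides | Gain, all 4 decide | Rejection, n = 36 | Rejection, n = 18 |
|---|---|---|---|---|---|
| 3 | 3 | 1.24 | 0.98 | 33% | 18% |
| 3 | 5 | 0.86 | 0.66 | 18% | 11% |
| 5 | 3 | 2.62 | 2.15 | 51% | 28% |
| 5 | 5 | 2.06 | 1.63 | 33% | 18% |

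When screening alone decides, simulated rejection is about 5%.

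**Judgement other than acuity.** Adding selection noise of SD 5 letters, to stand for dominance and the participant's view, at σ = 5, τ = 3: 16.67/√(25.67 + 25) × 0.798 = 1.87 letters instead of 2.62, with rejection about 27% at n = 36.

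**Per eye.** Half of each gain falls in each eye, so with the mean of three the treated eye shifts by 0.86/2 = 0.4 to 2.62/2 = 1.3 letters.

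**Testing the possible adjustments (n = 36).**

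- Pooled two-eye regression with each eye's baseline as covariate, assuming a between-participant SD of 8 letters: the slope is dominated by differences between participants and lies near 1 (0.92–0.97). About 1.1 of 1.24 letters and 2.3 of 2.62 letters remain.
- Within-pair regression (post-treatment between-eye difference on baseline between-eye difference, reading the intercept): when the mean of three chose the eye, bias is about 0 and rejection about 5%, at 1.6–1.7 times the standard error of the raw change.
- The same regression when screening alone chose the eye: bias about −0.6 to −1.1 letters.
- The same regression when all four readings chose the eye: over-correction of about 0.5–0.8 letters.

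**The case against.** The strongest reply is that the SAP already separates the two sets of readings: screening values stay out of the baseline, so an eye chosen at screening gives no bias. That stands. A reader might infer that nothing protects the baseline and that a spurious gain is bound to appear. The documents do not support that. Nor do they show that the choice is made late: the rule is printed under surgical technique, but its place in the Protocol does not date the decision, and preoperative procedures are referred to a study manual that is not available here. The bias is conditional on baseline-visit or reused clinic readings having informed the choice.

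Second, no paired test on change is planned. Analyses are descriptive, the mixed model is optional, no formal hypothesis is tested (SAP 1.2) and 0.05 is nominal. This also stands, so the rejection rates are illustrative. A biased descriptive mean is still biased, however. Nor does the SAP say that the model's response is change from baseline. If post-treatment values alone were compared, then with the mean of three deciding the null contrast would be about −1.4 to −3.6 letters, against the vector, because the true gap no longer cancels. A reader should not infer that every between-eye analysis favours the vector; only the change-based one does.

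Third, acuity is one of 18 outcomes in SAP 2.2, and the bias does not carry over to measures whose errors are independent of the choosing readings. It might also be inferred that a 15-letter safety loss could be hidden; a treated-eye shift of 0.4–1.3 letters makes that negligible.

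What survives is the gap itself. The screening exclusion says nothing about baseline-visit readings or reused clinic results that helped pick the eye.

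**Conclusion.** The point holds in conditional form. If readings that form the baseline also helped choose the eye, acuity change from baseline can show a spurious treated-minus-fellow gain of about 0.9–2.6 letters when the mean of three baselines decides, or about 0.7–2.2 letters when all four readings decide. The first case corresponds to illustrative rejection of about 18–51% at n = 36 and 11–28% at n = 18. The gain is zero if screening alone decides, and dominance and participant judgement shrink it. All of this rests on assumed SDs of 3–5 letters and independent errors. Readings taken on one day may share error, in which case averaging them removes less of it. The point concerns mainly acuity, and which readings actually chose the eye cannot be settled from the documents.

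**What to change.** Leave the clinical criterion for choosing the eye unchanged.

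1. **Protocol 5.4.2.2.2:** record and date the choice of eye and the acuity readings that informed it, before baseline visits 2–4 for any participant not yet treated. SAP 1.2 describes dosing in the past tense, so for most participants this may mean establishing it from source notes.
2. **SAP 3.2:** state that no acuity reading used to choose the eye, including a reused clinic result, enters that participant's baseline.
3. **SAP 6.2:** for participants whose eye was chosen on the baseline readings, add a sensitivity analysis that regresses the between-eye post-treatment difference on the between-eye difference in those baseline readings. Do not use a pooled two-eye model with each eye's baseline as covariate, which leaves most of the bias. Do not apply the within-pair adjustment where screening alone chose the eye. Where all four readings did, report it with its known over-correction.

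The cost is wording and one extra analysis, with no new test or visit. The within-pair estimate is less precise (about 1.6–1.7 times the standard error), and some participants' baselines will rest on fewer readings.
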